### 6.2.3.1 Bayesian dose-exposure model

The Bayesian linear model will estimate the dose-exposure relationship for PDR001 in order to guide the dose recommendation. The pharmacokinetic profiles of pembrolizumab and

nivolumab are similar, as expected considering that both are naked monoclonal antibodies that bind to the same target (Patnaik 2012, Robert 2014, Brahmer 2012), and the pharmacokinetic profile of PDR001 is expected to be similar. Based on the exposure data reported for pembrolizumab and nivolumab at their approved doses of 2 mg/kg and 3 mg/kg, respectively (pembrolizumab US label; nivolumab US label), a PDR001  $AUC_{(0-336h)} \geq 1000 \mu\text{g} \cdot \text{day/mL}$  at cycle 3 is expected to provide antitumor activity comparable to that of pembrolizumab and nivolumab.

A Bayesian linear model will be used to estimate the dose-exposure relationship for PDR001 in order to guide the dose recommendation to achieve a PDR001  $AUC_{(0-336h)} \geq 1000 \mu\text{g} \cdot \text{day/mL}$  in cycle 3, as described in Section 14.3.1.4. The dose-exposure relationship will be evaluated only when sufficient exposure data are available.

### 6.2.3.2 Bayesian logistic regression model of DLT rate

The adaptive Bayesian methodology provides an estimate of DLT rate for all dose levels of PDR001 that do not exceed the MTD and incorporates all accumulated DLT information from all dose cohorts for this estimation. In general, the next dose will have the highest chance that the DLT rate will fall in the target interval [16-33%) and will always satisfy the EWOC principle (less than 25% probability that the DLT rate is  $\geq 33\%$ ). In all cases, the dose for the next cohort will not exceed a 334% (1/2 log) increase from the previous dose. Smaller increases in dose may be recommended by the Investigators and Sponsor upon consideration of all of the available clinical data.

If the first 2 patients in a cohort experience a DLT, further enrollment to that cohort will stop and the BLRM will be updated with this new information. Re-evaluation of the available safety, PK, and PD data will occur. By incorporating information gained at the preceding dose levels, additional patients may be enrolled at this dose level or a lower dose level as agreed by Investigators and Novartis personnel and if the BLRM predicts that the risk that this dose exceeds the MTD remains below 25% (EWOC).

Dose escalation will continue until identification of the RP2D, which is expected to occur before the MTD is reached. However, dose escalation will stop when the MTD is reached, even if the exposure criteria for the RP2D have not been met.

The MTD is identified when the following 3 conditions are met:

1. at least 6 patients have been treated at this dose
2. this dose satisfies one of the following conditions:
  - a. the posterior probability of targeted toxicity at this dose exceeds 25% and is the highest among potential doses, or
  - b. minimum of 21 patients have already been treated on the trial to identify the MTD. Recommendation of RP2D may be made with fewer patients, prior to identification of MTD.
3. it is the maximum dose recommended for patients, either per the model or by review of all clinical data by Novartis and Investigators in a dose-escalation teleconference see Section 6.2.3.3.

To better understand the safety, tolerability and PK of PDR001, additional cohorts of patients may be enrolled at preceding dose levels, or to intermediate dose levels before or while proceeding with further dose escalation. Multiple dose levels may be evaluated in simultaneous cohorts, as long as none exceeds the maximum dose permitted by the BLRM, and a maximum of 6 patients are treated at a dose level greater than the highest dose previously shown to be safe. Depending on the  $AUC_{(0-336h)}$  and predicted DLT rate, it is possible that the dose will not be escalated above the starting dose of 1 mg/kg, and it is possible that doses greater than required to achieve the target exposure will be explored as long as they do not exceed the maximum dose permitted by the BLRM.

If a decision is made to escalate to a higher dose level but one or more additional patient(s) treated at the preceding dose level experiences a DLT during the first cycle of treatment, then the BLRM will be updated with this new information before any additional patients are enrolled at that higher dose level. Patients ongoing will continue treatment at their assigned dose levels.

### **6.2.3.3 Implementation of dose escalation decisions**

To implement dose escalation decisions, the available toxicity information (including AEs and laboratory abnormalities that are not DLTs), the recommendations from the Bayesian linear model and the BLRM, and the available PK and PD information will all be evaluated by the Investigators and Novartis study personnel (including the study physician and statistician) during a dose decision meeting by teleconference. Drug administration at the next higher dose level may not proceed until the investigator receives written confirmation from Novartis indicating that the results of the previous dose level were evaluated and that it is permissible to proceed to a higher dose level.

### **6.2.3.4 Intra-patient dose escalation**

For patients enrolled in the Phase I part of the study, intra-patient dose escalation is not permitted at any time within the first 4 cycles of treatment. After cycle 4 is completed, individual patients may be considered for treatment at a dose of PDR001 higher than the dose to which they were initially assigned and/or a different dosing regimen. In order for a patient to be treated at a higher dose of PDR001, he or she must have tolerated the lower dose for at least 4 cycles of therapy (i.e. he or she must not have experienced any PDR001-related toxicity CTCAE grade  $\geq 2$  at the lower dose originally assigned). Moreover, the new, higher dose with which the patient is to be treated must be a dose that has completed evaluation and has not exceeded the maximum tolerated dose (MTD). There is no limit to the number of times a patient may have his or her dose of PDR001 increased. For any further increase after the initial intra-patient dose escalation, the following rules apply: the patient must have experienced no CTCAE grade  $\geq 2$ , PDR001-related toxicity over at least two cycles of therapy at the lower dose, and the higher dose being considered must have been fully evaluated and shown not to exceed the MTD. Consultation and agreement with Novartis must occur prior to any intra-patient dose escalation occurring. These changes must be recorded on the Dosage Administration Record eCRF. Data from the first cycle of treatment at the new dose level will not be formally included in the statistical model describing the relationship between dose and occurrence of DLT. However, these data will be incorporated into the clinical assessment of safety during dose escalation teleconferences.

For patients enrolled in the phase II part of the study, intra-patient dose escalation or change in dosing regimen is not permitted.

#### 6.2.4 Definitions of dose limiting toxicities (DLTs)

A DLT is defined as an AE or abnormal laboratory value of CTCAE grade  $\geq 3$  assessed as unrelated to disease, disease progression, inter-current illness or concomitant medications, which occurs within the first cycle of treatment with PDR001 during the dose escalation part of the study, with the exceptions described in Table 6-3.

National Cancer Institute Common Terminology Criteria for Adverse events (NCI CTCAE) version 4.03 will be used for all grading. For the purpose of dose-escalation decisions, DLTs will be considered and included in the BLRM.

The investigator must notify the Sponsor immediately of any unexpected CTCAE grade  $\geq 3$  AEs or laboratory abnormalities. Prior to enrolling patients into a higher dose level, CTCAE grade  $\geq 2$  AEs will be reviewed for all patients at the current dose level.

**Table 6-3 Criteria for defining dose limiting toxicities**

DLTs include any AE of CTCAE grade 3 or higher occurring in cycle 1, during the dose escalation part of the study, for which relationship to study treatment cannot be ruled out, with the following exceptions:	
Hematology	Neutropenia is a DLT if it is CTCAE grade 4. Thrombocytopenia is a DLT if it is CTCAE grade 4. Anemia is a DLT if it is CTCAE grade 4. Lymphopenia is a DLT if it is CTCAE grade 4.
Hepatic	$\geq$ CTCAE grade 2 total bilirubin with $\geq$ CTCAE grade 2 ALT is a DLT.
Gastrointestinal	Nausea and vomiting are DLTs if they are $\geq$ CTCAE grade 3 for $>$ 2 days despite optimal anti-emetic therapy. Diarrhea is a DLT if it is $\geq$ CTCAE grade 3 for $>$ 2 days despite optimal anti-diarrhea treatment.
Pneumonitis	CTCAE grade 2 pneumonitis is a DLT if it persists $>$ 7 days despite treatment with corticosteroids. Grade 3-4 pneumonitis of any duration is a DLT.
Hypertension	CTCAE grade 3 hypertension is a DLT if it persists $>$ 7 days despite treatment. Grade 4 hypertension of any duration is a DLT.
Infection	CTCAE grade 3 infection or fever in the absence of neutropenia are DLTs if they persist $>$ 5 days. Grade 4 infection of any duration is a DLT.
Electrolytes	CTCAE grade 3 electrolyte abnormalities are DLTs if they persist $>$ 7 days despite treatment or are clinically significant. Grade 4 electrolyte abnormality of any duration is a DLT.
Rash and/or photosensitivity	$\geq$ CTCAE grade 3 rash or photosensitivity are DLTs if they persist $>$ 7 days despite treatment.
Fatigue	Fatigue is a DLT if it is $\geq$ CTCAE grade 3 and lasts $>$ 7 days.
Immune related toxicities (except pneumonitis)	CTCAE grade 3 immune related toxicities are DLTs if they persist $>$ 7 days despite treatment with corticosteroids. Immune related toxicities CTCAE grade 4 of any duration are DLTs.
Other AEs	Other clinically significant toxicities, including a single event or multiple occurrences of the same event that lead to a dosing delay of $>$ 7 days in cycle 1, may be considered to be DLTs by the Investigators and Novartis, even if not CTCAE grade 3 or higher.

## 6.3 Dose modifications

### 6.3.1 Dose modification and dose delay

For patients who do not tolerate the protocol-specified dosing schedule, dose or schedule adjustments are permitted in order to allow the patient to continue the study treatment. The following guidelines need to be applied:

- For clinical management of suspected immune-related events, reference to consensus management guidelines is recommended such as those provided in the National Comprehensive Cancer Network (NCCN) Guidelines for the Management of Immunotherapy-Related Toxicities (available at: [nccn.org/professionals/physician\\_gls/default.aspx#immunotherapy](http://nccn.org/professionals/physician_gls/default.aspx#immunotherapy)), the American Society of Clinical Oncology clinical practice guideline for Management of Immune-Related Adverse Events in Patients Treated with Immune Checkpoint Inhibitor Therapy (Brahmer 2018) or the European Society for Medical Oncology (ESMO) Clinical Practice Guidelines for Management of Toxicities from Immunotherapy (Haanen 2017). Note that in general, study treatment should be interrupted for grade 3 and 4 toxicities and for a subset of lower grade toxicities.
- Consider early referral to specialists with expertise in the diagnosis and management of immune-related AEs to thoroughly investigate events of uncertain etiology.
- Events not included in the study protocol or the reference guidance documents should be managed per institutional preference.
- A decision to resume treatment following the occurrence of a DLT, grade 3 or 4 or serious adverse suspected immune-related events that occur after the DLT period may be taken only after documented discussion with the Novartis medical monitor.

If more than 2 consecutive doses have to be skipped due to PDR001-related toxicities, then the patient must be discontinued from the study treatment. If a patient who misses more than 2 consecutive doses due to a PDR001-related toxicity is experiencing clinical benefit, and in the opinion of the investigator it is in the patient's best interest to remain on study, then the patient may continue treatment after discussion with Novartis.

Patients who discontinue the study for a study related AE or a study-related abnormal laboratory value must be followed as described in [Section 6.3.2](#).

All interruptions or change to study drug administration must be recorded on the Dose Administration Record eCRF.

### 6.3.2 Follow-up for toxicities

Patients whose treatment is interrupted or permanently discontinued due to an AE or clinically significant laboratory value, must be followed-up at least once a week (or more frequently if required by institutional practices, or if clinically indicated) for 4 weeks, and subsequently at approximately 4-week intervals, until resolution or stabilization of the event, whichever comes first. Appropriate clinical experts should be consulted as deemed necessary. In case of a suspected autoimmune disease AE, the relevant immunological assessments (e.g. rheumatoid factor, anti-DNA Ab, etc.) should be performed. In case of a toxicity suspected to be a cytokine release syndrome, the assessments outlined in [Section 7.2.2.5.6](#) must be performed. All patients

must be followed up for AEs and SAEs for 150 days following the last dose of PDR001. [Table 6-4](#) outlines the follow-up evaluation recommended for selected toxicities.

**Table 6-4 Follow-up evaluations for selected toxicities**

TOXICITY	FOLLOW-UP EVALUATION AND TREATMENT RECOMMENDATIONS
Infusion Reaction or hypersensitivity reaction	
Grade 1	Decrease infusion rate until recovery of the symptoms.
Grade 2	Stop infusion immediately, and keep line open. Follow institutional guidelines for the management and follow-up of infusion reaction. Restart infusion at 50% of previous rate under continuous observation. Ensure that there is a minimum observation period of 1 hour prior to restarting the infusion.
Grades 3 and 4	If the AE recurs at the reinitiated slow rate of infusion, and despite oral pre-medication, then permanently discontinue study treatment. Discontinue infusion immediately, and discontinue study treatment. Provide supplemental oxygen, fluids, and other resuscitative measures as needed. Monitor vital signs (e.g., blood pressure, pulse, respiration, and temperature) every 15 ± 5 minutes until resolution.
Cytokine Release Syndrome (CRS)	
Grade 2	See instructions for Grade 2 Infusion Reaction above.
Grade 3 or Grade 4	Discontinue study treatment. Follow-up CRS as per institutional guidelines. Take blood for cytokine measurements as specified in Section 7.2.2.5 Laboratory evaluations
Ocular (uveitis, eye pain, blurred vision)	
Grade 1	Continue study treatment without dose modification. Ophthalmology consultation.
Grade 2	Hold study treatment. Urgent ophthalmology consultation. Upon resolution to ≤ Grade 1 may consider resuming study treatment without dose reduction after discussion with the Novartis Medical Monitor and in consultation with ophthalmology.
Grade 3 or Grade 4	Discontinue study treatment. Urgent ophthalmology consultation.
Pulmonary (Pneumonitis)	
Grade 1	Consider study treatment hold. Manage per institutional practice. Consider resuming study treatment upon radiographic evidence of improvement.
Grade 2	Hold study treatment. Pulmonary and infection workup. Upon resolution to ≤ Grade 1, may resume study treatment without dose modification.
Grades 3 and 4	Discontinue study treatment.
Cardiovascular	
ECG QTc-Interval prolonged; hypertension	
Grade 3	Hold study treatment. Upon resolution to Grade ≤ 1 or baseline (hypertension, QTc) or < 30 msec difference from baseline (QTc) within ≤ 7 days, may resume study treatment without dose modification after discussion with the Novartis Medical Monitor. Baseline ECG refers to ECG(s) collected at screening.
Grade 4	Discontinue study treatment.

TOXICITY	FOLLOW-UP EVALUATION AND TREATMENT RECOMMENDATIONS
Other cardiovascular disorders	
Grade 2 (except myocarditis)	Hold study treatment. Upon resolution to Grade $\leq$ 1 or baseline, may resume study treatment without dose modification after discussion with the Novartis Medical Monitor.
Grade 2 myocarditis, or Grade $\geq$ 3 other cardiac disorders related to study treatment	Discontinue study treatment.
Gastrointestinal	
Diarrhea/colitis*	
Grade 1	May continue study treatment without dose modification. Manage per institutional standard guidelines which could include anti-diarrheal treatment, consideration of corticosteroid therapy, and hydration.
Grade 2	Hold study treatment. GI consultation. Upon resolution to $\leq$ Grade 1 and tapering of steroid requirement to $\leq$ 10 mg prednisone per day, resume study treatment without dose modification after discussion with the Novartis Medical Monitor.
Grade 3	Hold study treatment. GI consultation. Upon resolution to $\leq$ Grade 1 and tapering of steroid requirement to $\leq$ 10 mg prednisone per day, consider resuming study treatment after discussion with the Novartis Medical Monitor.
Grade 4	Discontinue study treatment.
AST and/or ALT elevation	
Grade 2 AST and/or ALT	Hold study treatment. Manage per institutional practice. Upon resolution to $\leq$ Grade 1 or baseline, consider resuming study treatment without dose modification.
Grade 2 transaminitis with bilirubin $>$ 1.5 X ULN (unless Gilbert's syndrome)	Discontinue study treatment.
Grade 3 AST and/or ALT	Hold study treatment. Manage per institutional practices. Upon resolution to $\leq$ Grade 1 or baseline within 7 days, consider resuming study treatment without dose modification after discussion with the Novartis Medical Monitor. Otherwise, discontinue study treatment.
Grade 4 AST and/or ALT	Discontinue study treatment.
Isolated total bilirubin elevation**	
Grade 2	Hold study treatment. Upon resolution to $\leq$ Grade 1 or baseline, may continue study treatment without dose modification.
Grade 3	Hold study treatment. Upon resolution to $\leq$ Grade 1 or baseline, may consider resuming study treatment after discussion with the Novartis Medical Monitor.
Grade 4	See footnote **. Otherwise, discontinue study treatment.

TOXICITY	FOLLOW-UP EVALUATION AND TREATMENT RECOMMENDATIONS
Asymptomatic amylase and/or lipase elevation ***	
Grade 3 or Grade 4, not associated with symptoms or clinical manifestations of pancreatitis***	Continue study treatment. If levels do not resolve to ≤ Grade 2 within ≤ 14 days after the initial report, hold study treatment. Upon resolution to ≤ Grade 2, may resume study treatment without dose modification, after discussion with the Novartis Medical Monitor.
Pancreatitis	
Grade 2/radiologic evidence	Hold study treatment. Manage per institutional practice. Upon resolution to ≤ Grade 1, may resume study treatment without dose modification, if no clinical evidence of pancreatitis and after discussion with the Novartis Medical Monitor.
Grades 3 or Grade 4	Discontinue study treatment.
Renal	
Serum creatinine	
Grade 2	Hold study treatment. Manage per institutional practice. Upon resolution to ≤ Grade 1, may resume study treatment without dose modification after discussion with the Novartis Medical Monitor.
Grade 3 or 4	Discontinue study treatment.
Musculoskeletal	
Grade 2 or Grade 3	Hold study treatment. Consider resuming study treatment without dose modification upon resolution to ≤ Grade 1 with appropriate management.
Grade 4	Discontinue study treatment. In some cases, resuming study treatment may be considered after discussion with the Novartis Medical Monitor and consultation with a rheumatologist.
Endocrine	
Hypothyroidism or hyperthyroidism	
Grade 2	May continue study treatment without dose modification. Management according to institutional practice.
Grade 3	Hold study treatment. Upon resolution to Grade ≤ 1 with appropriate management, may resume study treatment without dose modification.
Grade 4	May resume therapy following resolution or control with physiologic hormone replacement.
Other endocrine disorders	
Grade 2 and Grade 3	Hold study treatment. Upon resolution to Grade ≤ 1 with appropriate management, may resume study treatment without dose modification.
Grade 4	Hold study treatment. Grade 4 treatment-related endocrinopathies, such as adrenal insufficiency, adrenocorticotrophic hormone (ACTH) deficiency, hyper- or hypothyroidism, or glucose intolerance, which resolve or are adequately controlled with physiologic hormone replacement (corticosteroids, thyroid hormones) or glucose-controlling agents, respectively, may not require discontinuation after discussion with and approval from the Novartis Medical Monitor.
Neurology	
Grade 1	Consider study treatment hold, particularly for clinical suspicion of Guillain-Barre syndrome, encephalitis, aseptic meningitis, transverse myelitis, or peripheral neuropathy.
Grade 2	Hold study treatment. In some cases, resuming study treatment may be considered after discussion with the Novartis Medical Monitor.

TOXICITY	FOLLOW-UP EVALUATION AND TREATMENT RECOMMENDATIONS
Grade 3 or Grade 4	Discontinue study treatment.
Dermatology (rash) Grade 1 Grade 2 Grade 3 or Grade 4 Bullous dermatitis Stevens-Johnson syndrome (SJS), or Lyell syndrome/toxic epidermal necrolysis (TEN)	Continue study treatment without dose modification. Topical steroids, antihistamines, topical emollients. Consider holding study treatment. Topical or oral steroids, antihistamines. If study treatment is held and resolution to $\leq$ Grade 1, resume study treatment without dose modification. Hold study treatment. Manage per institutional practice. After resolution to $\leq$ Grade 1, consider resuming study treatment after discussion with the Novartis Medical Monitor. Hold study treatment. Grade 1-2 bullous dermatitis: discussion with the Novartis Medical Monitor is required before considering resuming study treatment. Grade 3 bullous dermatitis: consider resuming therapy after expert consultation and documented discussion with the Novartis medical monitor. Grade 4 bullous dermatitis: discontinue study treatment. Permanently discontinue study treatment.
Hematology Neutropenia (ANC) Grade 3 or Grade 4 Febrile neutropenia Grade 3 or Grade 4 Thrombocytopenia Grade 3 Grade 4 Anemia Grade 3 or Grade 4 Lymphopenia Any grade	Hold study treatment. Upon resolution to $\leq$ Grade 2 or baseline within $\leq$ 7 days, resume study treatment without dose modification, after discussion with the Novartis Medical Monitor. Hold study treatment. Upon resolution of fever and improvement of neutropenia to $\leq$ Grade 2 or baseline, resume study treatment without dose modification, after discussion with the Novartis Medical Monitor. Hold study treatment. Upon resolution to $\leq$ Grade 2 or baseline, resume study treatment without dose modification. For Grade 3 associated with major bleeding, discontinue study treatment. Discontinue study treatment. Hold study treatment. Upon resolution to $\leq$ Grade 2 or baseline within 7 days, resume study treatment without dose modification. Treatment-related lymphopenia does not require study treatment hold or discontinuation.
Other laboratory adverse events, not specified elsewhere in table and not included in the consensus guidelines Grade 3	Hold study treatment. Upon resolution to $\leq$ Grade 1, resume study treatment without dose modification.

TOXICITY	FOLLOW-UP EVALUATION AND TREATMENT RECOMMENDATIONS
Grade 4	Isolated Grade 4 electrolyte abnormalities not associated with clinical sequelae and corrected after appropriate management within 72 hours of their onset do not require discontinuation. In the case of Grade 4 electrolyte imbalances associated with clinical sequelae, or not resolved to $\leq$ Grade 1 within 72 hours despite appropriate management, discontinue study treatment.
Other non-laboratory adverse events, not specified elsewhere in table and not included in the consensus guidelines	
Grade 2	Consider study treatment hold, at Investigator discretion. Upon resolution to $\leq$ Grade 1, resume study treatment without dose modification.
Grade 3	Hold study treatment. Upon resolution to $\leq$ Grade 1, resuming study treatment must be discussed with the Novartis Medical Monitor.
Grade 4	Discontinue study treatment.

All dose modifications should be based on the worst preceding toxicity.
 
*Note: anti-diarrheal medication is recommended at the first sign of abdominal cramping, loose stools or overt diarrhea.
 
**Note: If Grade 3 or 4 hyper-bilirubinemia is due to the indirect (non-conjugated) component only, and hemolysis as the etiology has been ruled out as per institutional guidelines (e.g., review of peripheral blood smear and haptoglobin determination), then delay study treatment until resolved <math>\leq</math> Grade 1, and resume study treatment at the discretion of the investigator.
 
***Note: A CT scan or other imaging study to assess the pancreas, liver, and gallbladder must be performed within one week of the first occurrence of any <math>\geq</math> Grade 3 of amylase and/or lipase.
	

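### Table 6-4 is less strict for Grade 3 than for Grade 2 AST/ALT elevation when bilirubin is also above 1.5 x ULN

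*Protocol*

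**What the plan says.** Protocol Section 6.3.2 introduces Table 6-4 as a table that "outlines the follow-up evaluation recommended for selected toxicities". Its AST/ALT block has four rows:

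- Grade 2 AST/ALT alone: hold, then consider resuming once values return to Grade 1 or lower, or to baseline.
- "Grade 2 transaminitis with bilirubin" above 1.5 x ULN, unless the patient has Gilbert's syndrome: discontinue.
- Grade 3 AST/ALT, with no mention of bilirubin: hold. If values return to baseline, or to Grade 1 or lower, "within 7 days, consider resuming study treatment without dose modification after discussion with the Novartis Medical Monitor. Otherwise, discontinue study treatment".
- The last row of the block, "Grade 4 AST and/or ALT": discontinue.

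The next block is headed "Isolated total bilirubin elevation", so it does not cover bilirubin that rises together with transaminases. A footnote to the table bases every dose modification on the worst preceding toxicity. Section 6.3.1 adds that a decision to resume after a DLT, or after a later Grade 3, Grade 4 or serious suspected immune-related event, "may be taken only after documented discussion with the Novartis medical monitor".

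**The concern.** A treatment-action table should not become more permissive as the same toxicity gets worse. Here the combined row is written for a single grade, and the next grade up has no counterpart. A site that follows the table row by row would stop PDR001 permanently at Grade 2 AST/ALT with raised bilirubin. At Grade 3 with the same bilirubin it could consider restarting.

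The stake is patient safety. A transaminase rise accompanied by a bilirubin rise is the pattern that the table itself singles out as reason to stop at Grade 2. Exclusion criterion 3 in Section 5.3 bars patients without Gilbert's syndrome whose total bilirubin exceeds 1.5 x ULN, so in an eligible patient of that kind a value above the cut arose after screening. Nothing statistical turns on this: ORR, the analysis sets, the DLT model and the sample size are unaffected.

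**Working it through.** There is no plan figure to reproduce. The check is to read every row and footnote of Table 6-4, and the sections around it, for a rule that fits Grade 3 AST/ALT with bilirubin above 1.5 x ULN in a patient without Gilbert's syndrome.

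**Stated action by grade**

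| AST/ALT grade | Bilirubin not above 1.5 x ULN | Bilirubin above 1.5 x ULN, no Gilbert's syndrome |
|---|---|---|
| 2 | Hold, consider resuming | Discontinue |
| 3 | Hold, consider resuming if recovered within 7 days and after Medical Monitor discussion; otherwise discontinue | The same row, since none is specific to raised bilirubin |
| 4 | Discontinue | Discontinue |

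Without the bilirubin rise, the actions tighten with grade. With it, they run discontinue, conditional hold, discontinue.

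**Does other text supply the missing rule?**

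1. *Bilirubin block.* It covers isolated elevation only, so it does not apply while AST/ALT is also raised.
2. *Worst-toxicity footnote.* It sends a patient whose worst grade is 3 to the Grade 3 row, away from the combined Grade 2 row.
3. *Recovery condition in the Grade 3 row.* The row names AST and ALT and sets no explicit requirement that bilirubin recover.
4. *Section 6.3.1.* Its general statement for Grade 3 and 4 toxicities is to interrupt treatment, and it requires a documented discussion before resuming. It does not require discontinuation.
5. *Table 6-3.* The hepatic DLT is defined with Grade 2 or higher for both bilirubin and ALT, so Grade 3 ALT is included. That table governs Cycle 1 of dose escalation only, and the Amendment 07 rationale states that Phase I was complete. It suggests what was meant but does not act as a backstop.

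**How two similar blocks are written.** Two other blocks use a qualifier to move a lower grade to discontinuation. Under other cardiovascular disorders, the entry starting "Grade 2 myocarditis, or Grade" also takes in treatment-related cardiac disorders of Grade 3 and above, so both discontinue. Under thrombocytopenia, the text reads "For Grade 3 associated with major bleeding, discontinue study treatment", and Grade 4 also discontinues. In both, the higher grade is at least as strict as the qualified lower grade.

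**Exposure.** From the Amendment 08 study status: 25 / 319 = 0.078, or 7.8% of treated patients still on treatment at 06-May-2019.

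**The case against.** Several points can be made for leaving the table alone.

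- *The table is a recommendation.* Section 6.3.1 also refers sites to external consensus guidelines for suspected immune-related events, and Section 7.1.4 tells the investigator to stop treatment when continuing would be detrimental. This stands as mitigation. The content of those guidelines is not in the documents, so they cannot be assumed either to close the gap or to be silent on it. General discretion is not a discontinue rule for this combination.
- *Grade 3 is not an open-ended hold.* The 7-day limit, the Medical Monitor discussion and the default to discontinue all lower the risk. This also stands. Even so, resumption remains possible at Grade 3 where the Grade 2 row rules it out.
- *A clinician would read the combined row as a minimum, as Table 6-3 does.* Probably many would. But a separate Grade 3 row exists, carries no bilirubin condition and expressly allows resumption, so literal compliance gives the more lenient answer.
- *A patient recovering from Grade 3 through Grade 2 with bilirubin still raised could be caught by the combined row.* The table does not say so, and the worst-toxicity footnote points the other way.
- *The table is not uniformly stricter with severity elsewhere.* Thyroid events at Grade 4 may resume on control with hormone replacement, whereas Grade 3 requires resolution to Grade 1 or lower; febrile neutropenia lacks the 7-day limit set for neutropenia. This is fair, and it confines the comparison above to the two qualified blocks. It does not justify the AST/ALT wording.
- *The 7.8% says nothing about how often this happens.* Agreed. Enrollment closed on 22-Mar-2018, and the number still on treatment after 06-May-2019 is not given.

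**Conclusion.** The point holds: Table 6-4 is wrong as written and should be corrected. For a patient without Gilbert's syndrome and with bilirubin above 1.5 x ULN, one of the three AST/ALT grades concerned (Grade 3, out of 2, 3 and 4) has no outright discontinue instruction, although the grade below and the grade above both do. No text in the protocol or SAP supplies the missing rule.

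This rests on a literal reading of the rows. The external guidelines cited in Section 6.3.1 could not be consulted. The frequency of the event is unknown, and the only available measure of reach is the 25 of 319 patients still on treatment at 06-May-2019. The existing safeguards reduce the practical risk without removing the inconsistency. The consequence is confined to patient-safety wording.

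**What to change.** In Table 6-4, reword the combined row to: *Grade 2 or higher AST and/or ALT with bilirubin > 1.5 x ULN (unless Gilbert's syndrome): discontinue study treatment.* Limit the Grade 3 hold-and-resume row to cases without that bilirubin rise. All three grades then lead to discontinuation, in line with the Grade 2 or higher form already used for the hepatic DLT. Table 6-3 needs no change.

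The cost is the wording of two rows, with no new assessments, patients or analyses. Under Section 12.1 the change still needs a written amendment with sponsor and ethics committee approval, and health authority approval where required. The Amendment 07 rationale refers to dose modification guidelines shared across PDR001 protocols, so the sponsor should also check whether the same row appears in those; the documents here do not show whether it does.
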